8.2.3.5. Excluded Concomitant Medications and Procedures

The following medications and procedures are prohibited during the study:

- Systemic treatment with any of the following metabolizing enzyme inhibitors is not permitted during this study. A DDI with a strong inhibitor would increase MLN2238 exposure.
 - Strong inhibitors of CYP1A2: fluvoxamine, enoxacin, ciprofloxacin
 - Strong inhibitors of CYP3A: clarithromycin, telithromycin, itraconazole, voriconazole, ketoconazole, nefazodone, and posaconazole
- Systemic treatment with any of the following metabolizing enzyme inducers should be avoided unless there is no appropriate alternative medication for the patient to use. A DDI with a strong inducer would decrease MLN2238 exposure.
 - Strong CYP3A inducers: rifampin, rifapentine, rifabutin, carbamazepine, phenytoin, and phenobarbital
 - The dietary supplements St John's wort and Ginkgo biloba are not permitted.
- Additional treatment or procedures prohibited during the study:
 - Adjuvant hormone therapy for breast or prostate cancer.
 - Bisphosphonates: Concomitant treatment with bisphosphonates will not be permitted.
 - Any antineoplastic treatment with activity against MM except for drugs in this treatment regimen.
 - Radiation therapy (the requirement for local radiation therapy generally indicates disease progression).
 - Platelet transfusions to help patients meet eligibility criteria are not allowed within 3 days before study drug dosing.

8.2.3.6. Permitted Concomitant Medications and Procedures

The following medications and procedures are permitted during the study:

- Antiemetics, including 5-HT3 serotonin receptor antagonists, may be used at the discretion of the investigator.
- Loperamide or other antidiarrheal should be used for symptomatic diarrhea at discretion of the investigator. The dose and regimen will be according to institutional guidelines. IVF should be given to prevent volume depletion.
- Growth factors (eg, granulocyte colony stimulating factor [G-CSF], granulocyte macrophage-colony stimulating factor [GM-CSF], recombinant erythropoietin) are permitted. Their use should follow published guidelines and/or institutional practice; however, alternative usage may be reviewed with the Millennium Clinical or Medical

Representative . Erythropoietin will be allowed in this study. Their use should follow published guidelines and/or institutional practice.

- Patients should be transfused with red cells and platelets as clinically indicated (except as noted in 8.2.4) and according to institutional guidelines.
- Antiviral therapy such as acyclovir may be administered if medically appropriate.
- Patients who experience worsening neuropathy from baseline may be observed for recovery, and have dose reductions/delays as indicated in the protocol, and any supportive therapy or intervention may be initiated as appropriate at the discretion of the investigator.
- Supportive measures consistent with optimal patient care may be given throughout the study.

8.2.4. Precautions and Restrictions

Fluid deficits should be corrected before and throughout treatment.

Nonsteroidal anti-inflammatory drugs (NSAIDs) induced prevalence of nephrotoxicity is relatively low; however, given the wide use of these agents many persons are at risk, including for example, patients with cardio-renal disease, dehydration, and the aging kidney. NSAIDs should be avoided with impaired renal function given reported NSAID-induced renal failure in patients with decreased renal function.

Pregnancy

It is not known what effects ixazomib has on human pregnancy or development of the embryo or fetus. Therefore, female patients participating in this study should avoid becoming pregnant, and male patients should avoid impregnating a female partner. Nonsterilized female patients of reproductive age group and male patients should use effective methods of contraception through defined periods during and after study treatment as specified below.

Female patients must meet 1 of the following criteria:

- Postmenopausal for at least 1 year before the screening visit, OR
- Surgically sterile, OR
- If they are of childbearing potential, agree to practice 2 effective methods of contraception, at the same time, from the time of signing the informed consent form through 90 days after the last dose of study drug, AND
- Agree to practice true abstinence when this is in line with the preferred and usual lifestyle of the subject. (Periodic abstinence [eg, calendar, ovulation, symptothermal, post-ovulation methods] and withdrawal are not acceptable methods of contraception.)

Male patients, even if surgically sterilized (ie, status postvasectomy), must agree to 1 of the following:

- Agree to practice effective barrier contraception during the entire study treatment period and through 90 days after the last dose of study drug, OR
- Agree to practice true abstinence when this is in line with the preferred and usual lifestyle of the subject. (Periodic abstinence (eg, calendar, ovulation, symptothermal, post-ovulation methods] and withdrawal are not acceptable methods of contraception.)

8.2.5. Management of Clinical Events

Adverse drug reactions such as thrombocytopenia, diarrhea, fatigue, nausea, vomiting, and rash have been associated with ixazomib treatment. Management guidelines regarding these events are outlined below. Further details of management of ixazomib AEs are described in Section 6 of the ixazomib IB.

Transverse Myelitis

Transverse myelitis has also been reported with ixazomib. It is not known if ixazomib causes transverse myelitis; however, because it happened to a patient receiving ixazomib, the possibility that ixazomib may have contributed to transverse myelitis cannot be excluded.

Prophylaxis Against Risk of Infection

If lymphopenia is noted, patients may be at an increased risk of infection. In particular, lymphopenia can be associated with reactivation of herpes zoster and herpes simplex viruses. Antiviral therapy such as acyclovir or valacyclovir may be initiated as clinically indicated. Other antivirals are also acceptable.

Nausea and/or Vomiting

Standard anti-emetics, including 5-HT₃ antagonists, are recommended for emesis occurring upon treatment initiation; prophylactic anti-emetics may also be considered. Dexamethasone should not be administered as an anti-emetic. Fluid deficits should be corrected before initiation of study drug and during treatment.

Diarrhea

Diarrhea should be managed according to clinical practice, including the administration of antidiarrheals once infectious causes are excluded. Fluid intake should be maintained to avoid dehydration. Fluid deficits should be corrected before initiation of treatment and during treatment. Prophylactic antidiarrheals are not generally recommended.

Erythematous Rash With or Without Pruritus

As with bortezomib, rash with or without pruritus has been reported with ixazomib, primarily at the higher doses tested and when given with agents where rash is an overlapping toxicity. The rash may range from limited erythematous areas, macular and/or small papular bumps that may or may not be pruritic over a few areas of the body, to a more generalized eruption that is predominately on the trunk or extremities. Rash has been most commonly characterized as maculopapular or macular. To date, when it does occur, rash is most commonly reported within the first 3 cycles of therapy. The rash is often transient, self-limiting, and is typically Grade 1 to 2 in severity.

Symptomatic measures such as antihistamines or corticosteroids (oral or topical) have been successfully used to manage rash and have been used prophylactically in subsequent cycles. The use of a topical, IV, or oral steroid (eg, prednisone \leq 10 mg per day or equivalent) is permitted. Management of a Grade 3 rash may require intravenous antihistamines or corticosteroids. Administration of ixazomib (and/or other causative agent if given in combination) should be modified per protocol and re-initiated at a reduced level from where rash was noted (also, per protocol).

In line with clinical practice, dermatology consult and biopsy of Grade 3 or higher rash or any SAE involving rash is recommended. Prophylactic measures should also be considered if a patient has previously developed a rash (eg, using a thick, alcohol-free emollient cream on dry areas of the body or oral or topical antihistamines). A rare risk is Stevens-Johnson Syndrome, a severe and potentially life-threatening rash with skin peeling and mouth sores, which should be managed symptomatically according to standard medical practice. Punch biopsies for histopathological analysis are encouraged at the discretion of the investigator.

Thrombocytopenia

Blood counts should be monitored regularly as outlined in the protocol with additional testing obtained according to standard clinical practice. Thrombocytopenia may be severe but has been manageable with platelet transfusions according to standard clinical practice. Ixazomib administration should be modified as noted as per dose modification recommendations in the protocol when thrombocytopenia occurs. Therapy can be reinitiated at a reduced level upon recovery of platelet counts. A rare risk is thrombotic thrombocytopenic purpura (TTP), a rare blood disorder where blood clots form in small blood vessels throughout the body characterized by thrombocytopenia, petechiae, fever, or possibly more serious signs and symptoms. TTP should be managed symptomatically according to standard medical practice.

Neutropenia

Neutropenia has been reported with ixazomib. Blood counts should be monitored regularly as outlined in the protocol with additional testing obtained according to standard clinical practice. Neutropenia may be severe but has been manageable with G-CSF according to standard clinical practice. Neutropenic nadirs commonly recover without intervention by the beginning of the next scheduled cycle or with a short delay in treatment. ixazomib administration should be modified when neutropenia occurs, as noted in the dose modification recommendations table. Therapy can be reinitiated at a reduced level upon recovery of absolute neutrophil counts.

Fluid Deficits

Dehydration should be avoided because ixazomib may cause vomiting, diarrhea, and dehydration. Acute renal failure has been reported with ixazomib. Fluid deficits should be corrected before initiation of study drug and during treatment and as needed during therapy. Until further information is available, intake of NSAIDs while on this protocol should be avoided.

Hypotension

Symptomatic hypotension and orthostatic hypotension have been reported with ixazomib. Blood pressure should be closely monitored while the patient is on study treatment and fluid deficit should be corrected as needed, especially in the setting of concomitant symptoms such as nausea, vomiting, diarrhea, or anorexia. Patients taking medications and/or diuretics to manage their blood pressure (for either hypo- or hypertension) should be managed according to

standard clinical practice, including considerations for dose adjustments of their concomitant medications during the course of the trial.

Posterior Reversible Encephalopathy Syndrome

One case of posterior reversible encephalopathy syndrome (PRES) has been reported with ixazomib. While this case ultimately resolved, PRES has also been reported rarely with other proteasome inhibitors, VELCADE and Kyprolis. PRES is characterized by headache, seizures and visual loss, as well as abrupt increase in blood pressure. Prompt diagnosis and initiation of antihypertensive and anticonvulsant therapy are important to prevent irreversible end-organ damage.

8.2.6. Preparation, Reconstitution, and Dispensing

Ixazomib is an anticancer drug and as with other potentially toxic compounds caution should be exercised when handling ixazomib capsules.

Packaging and Labeling

The study drug ixazomib capsules will be provided by Millennium. The study drug will be handled as open-label material bearing a label with the following statement: "Caution: New Drug – Limited by Federal Law to Investigational Use."

The capsules are individually packaged using cold-form foil-foil blisters that are in a child-resistant carton. There are 3 capsules in each wallet/carton.

Storage, Handling, and Accountability

Study drug will be stored in the UAMS Research Pharmacy under the supervision of the research pharmacist who will be responsible for maintaining the supply according to the manufacturer's specifications, dispensing the drug for administration, and maintaining all accountability records.

Upon receipt at the investigative site, ixazomib should remain in the blister and carton provided until use or until drug is dispensed. The container should be stored at the investigative site refrigerated (36°F to 46°F, 2°C to 8°C). Ensure that the drug is used before the retest expiry date provided by Millennium. Expiry extensions will be communicated accordingly with updated documentation to support the extended shelf life.

Ixazomib capsules dispensed to the patient for take-home dosing should remain in the blister packaging and refrigerated as noted above until the point of use. The investigative site is responsible for providing the medication to the patient in the correct daily dose configurations. Comprehensive instructions should be provided to the patient in order to ensure compliance with dosing procedures. Patients who are receiving take-home medication should be given only 1 cycle of medication at a time. Patients should be instructed to store the medication refrigerated (36°F to 46°F, 2°C to 8°C) for the duration of each cycle. Patients should be instructed to return their empty blister packs to the investigative site, rather than discarding them. Reconciliation will occur accordingly when the patient returns for their next cycle of take-home medication. Any extreme in temperature should be reported as an excursion and should be dealt with on a case-by-case basis.

Because ixazomib is an investigational agent, it should be handled with due care. Patients should be instructed not to chew, break, or open capsules. In case of contact with broken

capsules, raising dust should be avoided during the clean-up operation. The product may be harmful by inhalation, ingestion, or skin absorption. Gloves and protective clothing should be worn during cleanup and return of broken capsules and powder to minimize skin contact.

The area should be ventilated and the site washed with soap and water after material pick-up is complete. The material should be disposed of as hazardous medical waste in compliance with federal, state, and local regulations.

In case of contact with the powder (eg, from a broken capsule), skin should be washed immediately with soap and copious amounts of water for at least 15 minutes. In case of contact with the eyes, copious amounts of water should be used to flush the eyes for at least 15 minutes. Medical personnel should be notified. Patients are to be instructed on proper storage, accountability, and administration of ixazomib, including that ixazomib is to be taken as intact capsules.

Study Compliance

Study drug will be administered or dispensed only to eligible patients under the supervision of the investigator or identified sub-investigator(s). The appropriate study personnel will maintain records of study drug receipt and dispensing.

Termination of Treatment and/or Study Participation

Patients will be informed that they have the right to withdraw from the study at any time for any reason, without prejudice to their medical care. The investigator also has the right to withdraw patients from the study for any of the following reasons:

- Adverse event
- Protocol violation
- Lost to follow-up
- Progressive disease
- Study terminated

At the time of withdrawal, all study procedures outlined for the End of Treatment visit should be completed (unless already completed and withdrawal is only from long-term follow-up for survival). The primary reason for patient's withdrawal from the study should be documented.

9. STATISTICAL AND QUANTITATIVE ANALYSES

9.1. Statistical methods

This is a single-arm, phase 2 study to evaluate bone remodeling during ixazomib treatment in relapsed/refractory MM patients. The primary objective is to evaluate the effect of ixazomib on inducing osteoblast activation as measured by change in osteocalcin from baseline to end of study. Ixazomib will be administered orally at the dosage of 4.0 mg weekly in a 28-day cycle for 6 cycles.

The study parameters of interest are described in Section 3. A similar study outlined in Zangari (16) by Terpos (30) evaluated bone markers after treatment with bortezomib in relapsed myeloma and found marked improvement. Terpos (30) reported the median and range osteocalcin level for myeloma patients at baseline and after 8 cycles of treatment with bortezomib. Based on an observed median osteocalcin level (and estimated standard deviation) of 7.46 ng/ml (sd = 12.65) in baseline myeloma patients compared to 19 ng/ml (sd = 18.6) after treatment with bortezomib, differences in pre- and post-

ixazomib continuous study parameters will be evaluated using a nonparametric Wilcoxon sign-rank test for paired data. The correlation between the pre and post treatment groups is assumed to be 0.5. Using the asymptotic relative efficiency method to define power of a nonparametric test relative to a one sample t test, and a significance level of 0.05, the design gives a power of 88% for 20 patients. If normality assumptions are met, then the paired t-test will be used. Difference in binary study parameters will be evaluated using McNemar's test for correlated proportions. Correlation between bone marker parameters will be evaluated using the Spearman correlation coefficient. One-sided pvalues <0.05 will be regarded as statistically significant.

The association between osteoblastic activation and myeloma response to ixazomib and to identify predictive factors for ixazomib-associated osteoblastic activation will be explored using differential expression analysis. All subjects meeting the eligibility criteria who have signed a consent form and have begun treatment will be evaluable for response, toxicities, and safety. Baseline and end of study descriptive statistics will be collected and analyzed per the statistical plan.

10.ADVERSE EVENTS

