1.1.4.5. Overview of the Oral Formulation of Ixazomib

The emerging safety profile indicates that oral ixazomib is generally well tolerated. The adverse events (AEs) are consistent with the class-based effects of proteasome inhibition and are similar to what has been previously reported with VELCADE though the severity of some, for example peripheral neuropathy, is less. While some of these potential toxicities may be severe, they can be managed by clinical monitoring and standard medical intervention, or, as needed, dose modification or discontinuation.

In the 4 ongoing studies (C16003, C16004, C16007, and C16009) investigating singleagent oral ixazomib in patients with differing malignancies (multiple myeloma, AL amyloidosis, nonhematologic cancers, and lymphoma), a total of 201 patients have been treated as of 27 March 2013. These patients have been treated with different doses of ixazomib as they are all phase 1 trials. An overview of the most frequent (at least 10%) AEs occurring in the pooled safety population from single-agent oral ixazomib Studies (C16003, C16004, C16007, and C16009) is shown in Table 3.

Primary System Organ	Oral Single Agent
Class Preferred Term	Total
	N = 201
	N (%)
Subjects with at Least One Adverse Event	197 (98)
Gastrointestinal disorders	160 (80)
Nausea	106 (53)
Diarrhoea	88 (44)
Vomiting	77 (38)
Constipation	46 (23)
Abdominal pain	33 (16)
General disorders and administration site conditions	151 (75)
Fatigue	103 (51)
Pyrexia	51 (25)
Oedema peripheral	27 (13)
Asthenia	31 (15)
Nervous system disorders	92 (46)
Headache	29 (14)
Dizziness	26 (13)
Neuropathy peripheral	21 (10)
Metabolism and nutrition disorders	107 (53)
Decreased appetite	64 (32)
Dehydration	37 (18)
Blood and lymphatic system disorders	98 (49)
Thrombocytopenia	68 (34)
Anaemia	42 (21)
Neutropenia	29 (14)
Lymphopenia	20 (10)
Skin and subcutaneous tissue disorders	90 (45)
Rash macular ^a	23 (11)
Musculoskeletal and connective tissue disorders	93 (46)
Back pain	24 (12)
Arthralgia	28 (14)
Respiratory, thoracic and mediastinal disorders	78 (39)
Cough	28 (14)
Dyspnoea	30 (15)
nfections and infestations	89 (44)
Upper Respiratory Infection	31 (15)

Source: Ixazomib Investigator's Brochure Edition 7

Abbreviations: MedDRA = Medical Dictionary for Regulatory Activities, version 15.0.

Subject Incidence: A subject counts once for each preferred term. Percentages use the number of treated subjects as the denominator.

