- Diagnosed or treated for another malignancy within 2 years before study enrollment or previously diagnosed with another malignancy and have any evidence of residual disease. Patients with non-melanoma skin cancer or carcinoma in situ of any type are not excluded if they have undergone complete resection.
- Patient has ≥ Grade 3 peripheral neuropathy, or Grade 2 with pain on clinical examination during the screening period.
- Participation in other clinical trials, including those with other investigational agents not included in this trial, within 21 days of the start of this trial and throughout the duration of this trial.

 Patients who have taken bisphosphonate or RANK Ligand Inhibitor within 3 weeks from screening.

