intervention to prevent 1 of the outcomes listed above, or involves suspected transmission via a medicinal product of an infectious agent. Examples of such medical events include allergic bronchospasm requiring intensive treatment in an emergency room or at home, blood dyscrasias or convulsions that do not result in inpatient hospitalization, or the development of drug dependency or drug abuse; any organism, virus, or infectious particle (eg, prion protein transmitting Transmissible Spongiform Encephalopathy), pathogenic or nonpathogenic, is considered an infectious agent.

Clarification should be made between a serious AE (SAE) and an AE that is considered severe in intensity (Grade 3 or 4), because the terms serious and severe are NOT synonymous. The general term *severe* is often used to describe the intensity (severity) of a specific event; the event itself, however, may be of relatively minor medical significance (such as a Grade 3 headache). This is NOT the same as *serious*, which is based on patient/event outcome or action criteria described above, and is usually associated with events that pose a threat to a patient's life or ability to function. A severe AE (Grade 3 or 4) does not necessarily need to be considered serious. For example, a white blood cell count of 1000/mm³ to less than 2000 is considered Grade 3 (severe) but may not be considered serious. Seriousness (not intensity) serves as a guide for defining regulatory reporting obligations.

Related

An event is "related" if more likely than not it was caused by the study drug

Unexpected

An event is "unexpected" when its specificity, nature, severity or incidence is not accurately reflected in the consent form, protocol, or IB previously reviewed and approved by the IRB. Examples include lower rate of response to treatment or a side effect that is more severe than initially expected.

Study Period

The study period is defined as the period of time from start of study drug through the End of Treatment visit. Events occurring after enrollment but prior to the study period will be considered pretreatment events (see above).

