10.2. Monitoring, Recording and Reporting of AEs

[name]., is the principal investigator of this study; The University of Arkansas for Medical Sciences (UAMS) is the study sponsor. UAMS is responsible for reporting serious adverse events (SAEs) to any regulatory agency; the principal investigator is responsible for reporting to the IRB and other entities (see Section 10.4).

AEs may be spontaneously reported by the patient and/or in response to an open question from study personnel or revealed by observation, physical examination, or other diagnostic procedures. When possible, signs and symptoms indicating a common underlying pathology should be noted as one comprehensive event. All AEs occurring during the study period must be recorded. The clinical course of each event should be followed until resolution, stabilization, or until it has been determined that the study treatment or participation is not the cause. SAEs that are still ongoing at the end of the study period must be followed up for up to 30 days to determine the final outcome. Any SAE that occurs after the study period and is considered to be possibly related to the study treatment or study participation should be recorded and reported immediately to the Sponsor (UAMS).

All subjects will be monitored for AE's during the study. Assessments may include monitoring the patient's clinical symptoms; laboratory, pathological, radiological, or surgical findings; physical examination; or other appropriate tests and procedures.

Planned hospital admissions or surgical procedures for an illness or disease that existed before the patient was enrolled in the trial are not to be considered AEs unless the condition deteriorated in an

unexpected manner during the trial (e.g., surgery was performed earlier or later than planned). All SAEs should be monitored until they are resolved or are clearly determined to be due to a patient's stable or chronic condition or intercurrent illness(es).

AE's are to be reported in a routine fashion at scheduled times during the trial, such as with the annual continuing review to the IRB. Certain AEs must be reported in an expedited manner to allow for more timely monitoring of subject safety and care. The preporting of these events depends on the characteristics of the event:

- Seriousness (grading of event)
- Relatedness to study therapy
- Expectedness

Steps to Determine if the event requires expedited Reporting:

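### Section 9.1 uses one evaluability rule for response and safety, so as written a dosed patient later found ineligible is outside the toxicity set (minor)

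*Combined protocol and SAP*

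**What the plan says.** Section 9.1 (Statistical methods) states one rule for all three purposes: "All subjects meeting the eligibility criteria who have signed a consent form and have begun treatment will be evaluable for response, toxicities, and safety". It has three joint conditions: eligible, consented, treatment begun. The document defines no separate safety or all-treated population. Intent-to-treat appears in the abbreviation list but is not used to define a set. Section 9.1 also mentions a statistical plan, but the combined document contains none beyond section 9.1 itself.

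The sections on collecting safety data do not use eligibility:

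- Section 10.1: "The study period is defined as the period of time from start of study drug through the End of Treatment visit".
- Section 10.2: "All AEs occurring during the study period must be recorded".
- Section 10.4: serious events go to the drug supplier from consent until 30 days after the last dose, whatever their causality or expectedness.

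On dosing, section 8.2.6 says: "Study drug will be administered or dispensed only to eligible patients under the supervision of the investigator". Section 8.2.1 repeats this limit and requires the criteria for giving drug to be satisfied and documented first. Neither section says how a patient found ineligible after dosing is handled in the analysis.

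**The concern.** A safety summary should describe everyone exposed to the drug. An eligibility condition can be reasonable for response, where the question concerns the intended population. It does not suit toxicity, because a patient who swallowed the capsule was at risk whether or not an entry criterion was met.

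Section 9.1 treats the two alike. An adverse event in a dosed but ineligible patient would be recorded under section 10.2 and, if serious, reported under section 10.4, yet that patient would be in neither the numerator nor the denominator of the toxicity rates. Membership of the set would also depend on a judgement about eligibility that can be made after the patient's toxicity is known. Eligibility rests on laboratory values, treatment history and washout intervals (sections 5.1 and 5.2), and such records can be corrected after the first dose.

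At stake is the accuracy of the descriptive toxicity rates in a trial of 20 patients, where each patient is 1/20 = 5% of the treated group.

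**Working it through.** The plan states no toxicity rate or safety-set size, so there is no figure of its own to reproduce. Its power statement does not involve the safety set and is unaffected.

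**Inputs**

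- Enrolment: 20 (section 4.2). All 20 are taken as dosed, which is an assumption.
- m, the number dosed and later found ineligible: not in the documents. Values of 0, 1 and 2 are assumed to show scale.
- k, the number of the 20 with a given toxicity, of whom j are among the m left out.

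**Step 1: who is counted.** Under section 9.1 the denominator is 20 − m, giving 20, 19 or 18. Under an all-dosed rule it is 20 in every case.

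**Step 2: change in a rate.** Change = (k − j)/(20 − m) − k/20.

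- Everyone left out had the event (j = m): change = −m(20 − k)/[20(20 − m)]. It is largest in size at k = m, where it equals −m/20.
- Nobody left out had the event (j = 0): change = +mk/[20(20 − m)]. It is largest at k = 20 − m, where it equals +m/20.

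The bound is therefore m/20 in either direction: 5.0 points for m = 1, 10.0 points for m = 2, zero for m = 0.

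**Step 3: examples**

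| All dosed | Left out | Section 9.1 rate | Change (points) |
|---|---|---|---|
| 1/20 = 5.0% | 1, with event | 0/19 = 0% | −5.0 |
| 2/20 = 10.0% | 1, with event | 1/19 = 5.3% | −4.7 |
| 2/20 = 10.0% | 1, without event | 2/19 = 10.5% | +0.5 |
| 2/20 = 10.0% | 2, both with event | 0/18 = 0% | −10.0 |
| 4/20 = 20.0% | 1, with event | 3/19 = 15.8% | −4.2 |

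**Step 4: against sampling error.** Exact (Clopper-Pearson) 95% intervals are 0.1% to 24.9% for 1/20 and 0% to 17.6% for 0/19. For 2/20 and 0/18 they are 1.2% to 31.7% and 0% to 18.5%. The change is smaller than the sampling uncertainty. It can still turn a toxicity that was seen into one reported as not seen.

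**Step 5: would a patient left out have events to lose?** In the single-agent table in section 1.1.4.5, the row "Subjects with at Least One Adverse Event" shows 197 of 201, or 98.0%. If that carries over, such a patient would very probably have adverse event data.

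**The case against.** The strongest reply is that the two sets coincide by design. Sections 8.2.1 and 8.2.6 confine dosing to eligible patients, so a treated patient should be an eligible one. Every adverse event is recorded and every serious event reported in any case. Sections 2 and 3 contain no safety objective or endpoint, and section 9.1 has no safety test or toxicity stopping boundary that uses the denominator. All of this stands, and it makes the point minor. It does not remove it: these are rules for conduct and collection, and none says who is counted when ineligibility comes to light after dosing.

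A second reply is that the sentence in section 9.1 says who is evaluable and does not expressly exclude anyone else. That is also fair. A reader might infer an explicit bar on ineligible patients, and the text contains none. But no other rule brings such a patient into the toxicity set, so applying the sentence literally leaves the patient out.

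Three stronger readings are tempting and are not supported:

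- **That safety data are lost.** They are not; sections 10.2 and 10.4 capture them. Only the summary rates are affected.
- **That a patient can become ineligible during treatment**, because an exclusion in section 5.2 bars participation in other trials "within 21 days of the start of this trial and throughout the duration of this trial". Section 5.2 is headed as a decision about enrolment. Joining another trial after dosing is more naturally an on-study deviation, and "Protocol violation" among the withdrawal reasons in section 8.2.6 says nothing about analysis sets.
- **That the protocol's background tables set the rule for this trial.** Their footnote, "Percentages use the number of treated subjects as the denominator", describes pooled results from other studies. It shows a familiar convention and imposes nothing here.

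**Conclusion.** The point holds as a minor wording defect. The one evaluability rule in section 9.1 makes eligibility a condition for the toxicity summary, and applied as written it leaves out a dosed patient later found ineligible.

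The effect is at most 5 percentage points on any toxicity rate for each patient left out of 20, in either direction, and zero if no ineligible patient is dosed. This assumes that all 20 enrolled patients are dosed. The number found ineligible is not in the documents, so one or two is an illustration and not a forecast. The osteocalcin endpoint, its test, the significance level and the sample size are unaffected. If a separate statistical plan exists and already defines safety by exposure, the remaining task is to bring section 9.1 into line with it.

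**What to change.** Split the sentence in section 9.1 in two. For safety and toxicity: the set is every patient who received at least one dose of ixazomib, whatever is later found about eligibility. For response: keep the present three conditions unchanged.

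The cost is one sentence in an amendment. It needs no new patients, samples, visits or data items, because sections 10.2 and 10.4 already collect what is required.
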